Note: If the patient qualifies based only on a LM lesion, then there must be involvement of the distal bifurcation (Medina 1,1,1) intended for treatment with a 2-stent approach (separate stents into the LAD and LCX) if randomized to PCI. However, if the patient also has non-LM disease in the RCA and/or non-ostial LAD and/or non-ostial LCX that requires separate treatment, any LM lesion is a valid criterion for enrollment, whether LM ostial, shaft or distal bifurcation disease, and any strategy of treating the LM may be employed, including not treating the ostial LCX, a provisional approach or a planned 2-stent strategy as appropriate. Similarly, if the patient qualifies based only on LAD-Dg disease, whether a bifurcation lesion or separate lesions in the LAD and Dg, without RCA or LCX disease, then both the LAD and Dg must be true lesions intended for stents (planned 2-stent approach). However, if the patient has LAD-Dg disease and a lesion in the RCA or LCX that also requires treatment, the LAD-Dg disease can then be treated in any fashion (2-stents, a provisional approach, or the Dg not even dilated if it is small), according to operator preference
5. Suitable candidate for both PCI with metallic DES and HCR as determined by clinical assessment and angiogram review by an interventional cardiologist and a cardiac surgeon at the enrolling clinical site
6. Ability to tolerate and no plans to interrupt dual anti-platelet therapy for \geq 6 months if presentation with stable CAD, or \geq 12 months if presentation with biomarker positive acute coronary syndrome (ACS)
7. Willing to comply with all protocol required follow-up

Exclusion Criteria

1. Previous cardiac surgery of any kind, including CABG
2. Previous thoracic surgery involving the left pleural space
3. Previous LM or LAD stent (a) with evidence of in-stent restenosis *or* (b) within 1 cm of a qualifying lesion
4. Previous PCI of the LM and/or LAD within 12 months prior to randomization
5. PCI with bare metal stent (BMS) within 12 months prior to randomization
6. Any complication or unsuccessful revascularization with PCI within 30 days prior to randomization.

Note: A patient may be considered eligible for enrollment if PCI with DES in non-

LM and non-LAD territory was performed within 30 days prior to randomization, as long as revascularization was successful and uncomplicated, or has been performed any time more than 30 days prior even if unsuccessful or complicated

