All patients enrolled in this trial will undergo coronary artery revascularization. Patients will be randomly assigned to the following treatment groups:

Hybrid Coronary Revascularization (HCR Group)

LIMA to LAD + PCI with metallic DES of non-LAD vessel(s)

Multi-vessel PCI (PCI-only Group)

Multi-vessel PCI with metallic DES, including the LAD and or LM

| Qualifying angiogram type | Time from the 3-vessel qualifying angiogram until randomization | Time from randomization to 1 st procedure | Sequence options if randomized to HCR | Sequence options if randomized to multi-vessel PCI | If staged: Time from first revascularization intervention after randomization until final planned revascularization intervention |
|--|---|--|---|--|--|
| 3-vessel angiogram only (PCI not performed) | Anytime within 90 days | ≤14 days after randomization | 
 1. Off-pump minimally invasive CABG first followed by staged PCI (recommended) 2. PCI first followed by staged Off-pump minimally invasive CABG 3. Concomitant Off-pump minimally invasive CABG and PCI (same calendar day) | 
 1. Single procedure multi-vessel PCI 2. Staged PCI procedures | No longer than 90 days (≤60 days recommended) |
| 3-vessel angiogram followed by PCI of a non-LM or non-LAD lesion in the same or subsequent procedure within 90 days prior to randomization | Anytime within 90 days | ≤14 days post randomization | 
 1. If only untreated LM or LAD lesion remains: Off-pump minimally invasive CABG 2. If non-LM or non-LAD lesion(s) remain: Same 3 options as above | 
 1. If only untreated LM or LAD lesion remains: single PCI procedure 2. If non-LM or non-LAD lesion(s) remain: Same 2 options as above | No longer than 90 days (≤60 days recommended) |

Patients will be randomly assigned (1:1) to HCR or multi-vessel PCI. The randomization procedure will be performed after patient eligibility is confirmed.

For patients identified in the setting of a qualifying 3-vessel diagnostic angiogram without a PCI performed during or subsequent to the diagnostic angiogram, randomization must occur within 90 days following the qualifying angiogram. The first study revascularization intervention is recommended to be performed within 72 hours post randomization and must be performed within 14 days following randomization (see above Table for possible procedure options).

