Note: Whenever PCI is performed after the LIMA-LAD revascularization, LIMA angiography must be performed prior to the PCI to assess the graft and distal anastomosis. Please see the Procedural Treatment Guidance Document for further recommendations as to when and how to intervene if the distal anastomosis appears abnormal and/or antegrade flow is reduced.

In most surgical specialties, minimally invasive surgery refers to the access the operator takes to the surgical field. Minimally invasive cardiac surgery, however, aims to ameliorate two potentially invasive surgical components: the cardiopulmonary bypass machine and the sternotomy incision. For the purpose of this trial, acceptable minimally invasive approaches to LIMA-LAD revascularization are sternal sparing off-pump procedures.

Listed below are definitions of the beating heart, sternal sparing minimally invasive operations that are acceptable for patients enrolled in this trial and randomly assigned to the HCR group. The selection of the HCR strategy below remains at the discretion of the surgical investigator. The chosen approach will be documented and reported for each patient in the trial.

Surgical Interventions

Off-Pump CABG

An off-pump CABG will be defined as an isolated LIMA-LAD revascularization performed on the beating heart without the use of cardiopulmonary bypass. Additional bypass grafts to other targets (including the diagonal) are not allowed in this study as part of an HCR procedure. For the trial, the planned minimally invasive approach to the LIMA – LAD revascularization must be a **sternal sparing off-pump procedure**. Planned open sternotomy will not be allowed in this study. However, after randomization, conversion of a planned sternal-sparing procedure to an open sternotomy procedure is acceptable if required to safely and successfully complete the revascularization procedure. Such conversions will be tracked.

The planned sternal-sparing, off-pump LIMA-LAD revascularization may be performed by Mid-CAB, Robotic- Assisted CAB, or TECAB as described below

1. Minimally Invasive Direct Coronary Artery Bypass (Mid-CAB)

A mid-CAB will be defined as any operation in which LIMA mobilization is undertaken in an open fashion through a limited anterior or lateral thoracotomy incision. The anastomosis will be performed by hand on the beating heart.

2. Robotic-Assisted Coronary Artery Bypass

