Only commercially available metallic drug-eluting stents may be used in this protocol. Because the use of DES on patients with left main disease or with three-vessel disease, both of which are off-label uses for DES, is considered investigational, this trial will be conducted under an Investigational Device Exemption (IDE). PCI should be performed using standard techniques at the discretion of the operator. In general PCI should be performed of lesions in vessels with visually estimated reference vessel diameter ≥ 2.25 mm with evidence of a) plaque rupture or thrombosis, or b) with an angiographic diameter stenosis $\geq 80\%$, or c) with evidence of ischemia on either non-invasive testing or by fractional flow reserve ≤ 0.80 or iFR ≤ 0.90 . Which of these criteria are met will be categorized. The specific adjunctive devices used (e.g. atherectomy, cutting/scoring balloons, or aspiration) and techniques (e.g. 1- vs. 2-stent and technique for treatment of bifurcation lesions) will be collected. Bioresorbable vascular scaffolds may not be used in this study.

Procedures may be staged at the discretion of the operator, but the intention to stage procedures must be specified within 24 hours after completion of the first procedure, should ideally be completed within 60 days of the first procedure, and in all cases must be completed within 90 of the first procedure after randomization.

For patients randomized to HCR, if off-pump CAB is performed first, prior to the staged PCI procedure a diagnostic angiogram of the LIMA-LAD graft must be performed, irrespective of the

Optimal Medical Management

All patients should be managed according to guideline-directed medical therapy (GDMT) by clinicians at each clinical site according to generally accepted societal recommendations. Details of GDMT are included in the MOP. Information will be collected about adherence to GDMT.

DEFINITIONS AND MEASUREMENT OF ENDPOINTS

Primary Endpoint

The primary endpoint for this trial is a composite of MACCE over 5 years following randomization.

All MACCE events will be adjudicated by an independent CEC. For the purpose of this trial **MACCE** is defined as a non-weighted composite score comprised of the following components:

- *All-cause mortality*
Death from any cause
- *Stroke*

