Planned staged procedures which are declared within 24 hours of the first revascularization procedure or post randomization and are performed within 90 days of the first post-randomization revascularization procedure will not be considered an unplanned revascularization. Staged procedures performed >90 days after the first post-randomization revascularization procedure, even if originally pre-specified, will be considered an endpoint unplanned revascularization. Intervention on the LIMA, LIMA-LAD distal anastomosis or LAD triggered by routine LIMA angiography prior to a planned staged PCI will not be considered an unplanned revascularization. However, if anterior ischemia occurs after CABG necessitating LIMA angiography prior to the planned staged PCI with subsequent intervention on the LIMA, LIMA- LAD distal anastomosis or LAD, this event will be adjudicated as an unplanned revascularization.

Secondary Endpoints

The secondary endpoints for the trial (each measured at 30 days post procedure, 12, 24, 36, 48, and 60 months, unless otherwise specified) of the trial include:

Cardiovascular Events (adjudicated)

- *MACCE* (defined above) at 30 days post procedure, and 12, 24, 36, 48 months
- *Individual components of MACCE (adjudicated, as defined above):*
 - All-cause mortality
 - Stroke
 - Myocardial infarction
 - Unplanned revascularization
- Ischemia-driven revascularization (*adjudicated*)
- *Cardiovascular and Non-cardiovascular Mortality (adjudicated)*
Cardiovascular mortality, as adjudicated by the CEC, will be assessed. Cardiovascular death includes sudden cardiac death, death due to acute MI, heart failure or cardiogenic shock, stroke, other cardiovascular causes, or bleeding. Non- cardiovascular death is defined as any death with known cause not of cardiovascular causes. Any deaths in which the cause is unknown or undetermined will be considered cardiovascular.
- *Stent thrombosis (adjudicated)*
Stent thrombosis will be adjudicated according to the Academic Research Consortium scale.²⁵ Stent thrombosis will be considered to be present if criteria for definite or probable stent thrombosis are met. According to its timing, stent thrombosis will be further classified as acute (<24 hours), subacute (24 hours – 30 days), early (≤ 30 days), late (> 30 days – 1 year), or very late (> 1 year).
- *Symptomatic graft stenosis or occlusion (adjudicated)*

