Symptomatic graft stenosis or occlusion requires angiographic confirmation of a DS $\geq 50\%$, and the presence of at least one of the following criteria: i) A positive functional study corresponding to the area served by the target lesion; or ii) Ischemic ECG changes at rest in a distribution consistent with the target vessel; or iii) Typical ischemic symptoms referable to the target lesion; or iv) IVUS of the target lesion with a minimal lumen area (MLA) of $\leq 4 \text{ mm}^2$; or v) FFR of the target lesion ≤ 0.80 or iFR of the target lesion ≤ 0.90 .
Intervention on the LIMA, LIMA-LAD distal anastomosis or LAD triggered by routine LIMA angiography prior to a staged PCI will also be considered to meet the criteria for symptomatic graft stenosis or occlusion.
The adjudicated rates of symptomatic graft stenosis or occlusion of the LIMA to the LAD in the HCR arm will be compared to the rate of angiographic definite stent thrombosis of LAD stents in the PCI arm.

Hospitalizations (non-adjudicated)

- Re-hospitalization will be assessed and classified as all-cause or cardiovascular (further subdivided as due to cardiac arrest, acute MI, heart failure or cardiogenic shock, other cardiovascular causes, or bleeding).

Bleeding (non-adjudicated)

- Site assessed bleeding complications will be reported using the Bleeding Academic Research Consortium (BARC) Scale²⁶:
 - **Type 0:** no bleeding
 - **Type 1:** bleeding that is not actionable and does not cause the patient to seek unscheduled performance of studies, hospitalization, or treatment by a healthcare professional; may include episodes leading to self-discontinuation of medical therapy by the patient without consulting a healthcare professional
 - **Type 2:** any overt, actionable sign of hemorrhage (eg, more bleeding than would be expected for a clinical circumstance, including bleeding found by imaging alone) that does not fit the criteria for type 3, 4, or 5 but does meet at least one of the following criteria: (1) requiring nonsurgical, medical intervention by a healthcare professional, (2) leading to hospitalization or increased level of care, or (3) prompting evaluation (this does not apply to routine evaluation of chest tube drainage).
 - **Type 3**
 - **Type 3a**
 - Overt bleeding plus hemoglobin drop of 3 to 5 g/dL (corrected for transfusion: 1 U packed red blood cells or 1 U whole blood = 1 g/dL hemoglobin or 3% hct), OR
 - Any transfusion with overt bleeding
 - **Type 3b**

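### The LAD durability comparison sets a broad graft-failure event in HCR against definite LAD stent thrombosis alone in PCI, so equal LAD failure is expected to look worse for HCR

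*Combined protocol and SAP*

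**What the plan says.** The comparison stands in the combined protocol and SAP, Definitions and Measurement of Endpoints, Secondary Endpoints, under Symptomatic graft stenosis or occlusion.

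- **HCR event, main route.** Angiographic diameter stenosis of at least 50% plus one of five criteria: positive functional study, resting ECG changes, typical symptoms, IVUS lumen area, or FFR/iFR.
- **HCR event, second route.** "Intervention on the LIMA, LIMA-LAD distal anastomosis or LAD triggered by routine LIMA angiography prior to a staged PCI will also be considered" to qualify. This route requires no symptom or ischemia.
- **PCI event.** The graft rate "will be compared to the rate of angiographic definite stent thrombosis of LAD stents in the PCI arm".

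The routine angiogram is prescribed under Hybrid Coronary Revascularization: "Whenever PCI is performed after the LIMA-LAD revascularization, LIMA angiography must be performed prior to the PCI". Percutaneous Interventions repeats it for surgery-first patients, and the table under Treatment Assignments recommends surgery first. No matching LAD angiogram is specified for the PCI arm.

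The stand-alone stent thrombosis endpoint is wider than the one used here: "Stent thrombosis will be considered to be present if criteria for definite or probable stent thrombosis are met". Analysis of Secondary End-points, Cardiovascular Events, assigns the stratified log-rank test to both endpoints. It does not say how two different endpoints form one comparison.

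**The concern.** An LAD stent with restenosis of at least 50%, angina and a positive FFR is not an event in this comparison. A LIMA graft with the same findings is. The two arms therefore report different quantities, and the difference between them mixes treatment durability with breadth of definition. The HCR arm also has a prescribed look at the graft, and what is repaired at that look counts.

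Durability of the LIMA-LAD graft relative to LAD stents is central to the rationale in Background and Significance, so the result will be read as evidence on that question. At stake is the interpretation of this secondary comparison, not the primary result.

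**Working it through.** The documents give no rate, power or sample size for this comparison, so there is no plan figure to reproduce. The direction follows from the definitions. The size can only be illustrated.

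**Events side by side**

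| Finding at the treated LAD | HCR | PCI |
|---|---|---|
| Stenosis of at least 50% plus an ischemia criterion | counted | not counted, unless definite thrombosis |
| Definite stent thrombosis | not applicable to a graft | counted |
| Probable stent thrombosis | not applicable to a graft | not counted |
| Repair prompted by routine angiogram before staged PCI | counted | no such angiogram specified |
| Silent failure, never imaged | not counted | not counted |

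Failure of a stent confined to the left main is also outside the PCI event. That gap is partial, because the inclusion note has left-main-only qualifiers receive "separate stents into the LAD and LCX" if randomized to PCI.

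**Inputs.** 2354 patients allocated 1:1 gives 2354/2 = 1177 per arm; tests are two-sided at 0.05 (Analysis Plan). Assumed: true LAD failure f, equal in both arms; share h of failures counted in HCR; share s counted in PCI.

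**Formulas.** Expected rates are p1 = h·f (HCR) and p2 = s·f (PCI), so the apparent risk ratio is h/s. The chance of a false significant result against HCR is P(Z > (1.96·SE0 − (p1 − p2))/SE1), where SE0 is the pooled and SE1 the unpooled standard error of a two-proportion test.

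**Worked case.** With f = 4%, h = 100% and s = 50%, p1 = 0.04 (47.1 events) and p2 = 0.02 (23.5 events).
- SE0 = √(2·0.03·0.97/1177) = 0.00703
- SE1 = √((0.04·0.96 + 0.02·0.98)/1177) = 0.00702
- (1.96·0.00703 − 0.02)/0.00702 = −0.89, which gives 81%.

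**Chance of a false result against HCR at f = 4% (nominal 2.5%)**

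| HCR share counted | PCI 75% | PCI 50% | PCI 25% |
|---|---|---|---|
| 100% | 26% | 81% | >99% |
| 75% | 2.5% | 34% | 93% |
| 60% | 0.2% | 10% | 75% |

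The first row applies when failure means the protocol's own graft criteria. The lower rows apply when failure also includes silent graft failures that are never imaged. At 60% against 75% the error reverses, with a 14% chance of a false result in favor of HCR. For the first row, f = 2% gives 15%, 51% and 91%; f = 6% gives 37%, 94% and >99%. An unstratified log-rank simulation of the first row at 4% (exponential times, 5 years, 15% loss) gave 25%, 78% and >99%. A stratified version with 125 sites and an assumed stratum mix gave 20%, 72% and >99%.

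**Routine-angiogram repairs alone**, with an otherwise common definition, f = 4% and repairs in an assumed 1% of HCR patients:
- Counted: 5% against 4%, risk ratio 1.25, false result against HCR in 21.5%.
- Left out, if all would later have become symptomatic: 3% against 4%, risk ratio 0.75, false result in favor of HCR in 26%.

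Neither treatment of these repairs is neutral.

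**The case against.** The strongest counterargument is that a symmetric endpoint already exists. Ischemia-driven unplanned revascularization applies nearly the same stenosis and ischemia criteria in both arms, with CEC adjudication and identification of target vessel and lesion whenever possible. Treated LAD restenosis in the PCI arm therefore counts there and in MACCE. This stands, and it limits the consequence. It does not repair the comparison at issue, which the plan states will be made.

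Further points that stand:
- The comparison is absent from the endpoint lists in the Abstract and under Endpoints.
- Every failure rate and counted share above is assumed. The false-positive figures also presume one formal between-arm test, whereas the text says only that the rates will be compared.
- HCR does not capture quite every LAD failure. A patient assigned to HCR whose LAD is stented instead has no graft to fail, and Power and Sample Size allows for such crossover.

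A reader might infer that HCR is bound to show the higher rate. The documents do not support that: the statement is about expectation, it needs some PCI failures to be restenosis, and the direction can reverse if many graft failures are silent. Nor do they support an inference that LAD restenosis goes uncounted in the trial.

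**Conclusion.** The comparison as written is not like with like, and nothing elsewhere in the plan supplies a matching PCI event. If LAD failure by the graft criteria is equally frequent in both arms, the expected HCR rate is higher whenever some PCI failures are restenosis rather than definite thrombosis. Under that assumption the apparent risk ratio is one divided by the share of PCI failures that are definite thrombosis: 2 at one half, 4 at one quarter. That share is not in the documents, so the size of the bias is unknown.

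It would be tempting to conclude that the trial's main result is biased against HCR. It is not: the primary MACCE definition and analysis do not use this comparison. The point is a should-fix on a secondary comparison.

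**What to change.** Replace the last sentence of the endpoint with a comparison of CEC-adjudicated symptomatic LAD failure, by intention to treat, timed from randomization, using the stratified log-rank test and one definition that does not depend on arm:

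- **Event.** Angiographic stenosis of at least 50%, occlusion or definite thrombosis of whatever study treatment the LAD received (LIMA graft, anastomosis or LAD stent, including LAD stents in HCR patients who cross over), plus at least one of the five existing criteria.
- **Boundary cases.** Handle diagonal lesions and left main stents by the same rule in both arms. Do not count a native lesion upstream of a patent graft.
- **Routine-angiogram repairs.** Show results with and without interventions triggered only by the routine LIMA angiogram, side by side, since leaving them out favors HCR and counting them favors PCI. The Unplanned Revascularization text already separates them from the case "if anterior ischemia occurs after CABG necessitating LIMA angiography prior to the planned staged PCI".
- **Fallback.** If restenosis that was not revascularized cannot be collected reliably, restrict the comparison to CEC-adjudicated ischemia-driven LAD target-vessel revascularization in both arms.
- **Descriptive reporting.** Give graft stenosis or occlusion and stent thrombosis (definite or probable) as separate rates, with no test of one against the other.

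The cost is revised endpoint wording, a small addition to CEC forms and source collection, and one extra analysis. The collection work is real: the CEC's charge is MACCE, source documents are gathered for MACCE and only some other events, and consent to core-laboratory film analysis does not by itself collect the films. Silent failures stay uncounted in both arms.
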